refractory disease was not significantly different from patients with chemosensitive disease. Various other investigators have retrospectively reported encouraging results with allogeneic HPCT in patients with relapsed and/or refractory Hodgkin's and NHL (13-18), none focusing primarily on refractory lymphomas.

A single institution study conducted at Ohio State University reported outcomes of allogeneic HPCT in patients with chemotherapy refractory aggressive NHL [19]. The study retrospectively analyzed outcomes of 46 patients with chemorefractory, aggressive NHL patients who had either stable disease (SD, n=32) or progressive disease (PD, n=14), respectively, following last salvage treatment. The median age was 46 years (range 22-63 yrs). 39 patients received matched sibling allografts, while 7 underwent unrelated donor transplantation. Diagnoses included diffuse large B-cell lymphoma (n=18), Burkitt's lymphoma (n=3), transformed B-cell lymphoma (n=5), mantle cell lymphoma (n=11) and peripheral T-cell lymphoma (n=9). The median number of prior therapies was 3 (range 2-8). Median follow-up of surviving patients is 5-years. 5-year overall survival (OS), progression free survival (PFS), and relapse rate for the whole cohort (n=46) were 38%, 34%, and 35% respectively. The rate of grade II-IV acute graft-versus-host disease (GVHD) was 43%. Of the 33 evaluable patients 75% developed chronic GVHD. Overall non-relapse mortality rate was 34%. The 5-year OS and PFS rates for patients with SD and PD were 46% vs. 21% (p-value=0.01; log-rank test), and 46% vs. 7% (p-value=0.0002; log-rank test) respectively. This study hints at potential of allogeneic transplant as curative therapy for a subset of chemorefractory patients with SD. These preliminary, encouraging results warrant confirmation in a well-designed clinical trial.

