Fred Hutchinson Cancer Research Center reported outcome of nonmyeloablative allogeneic HPCT for chemotherapy-refractory indolent or transformed NHL [21]. Sixty-two patients with indolent or transformed NHL were treated with allogeneic HPCT from related (n = 34) or unrelated (n = 28) donors after conditioning with 2 Gy of total-body irradiation with or without fludarabine. Nine unrelated donors were mismatched for \geq one HLA antigen. Sixteen patients had histologic transformation before HPCT. 63% of patients had chemotherapy sensitive disease at transplantation, while 23% were chemotherapy refractory and 14% had an untreated relapse. Median age was 54 years, and patients had received a median of six lines of treatment before HPCT. Median follow-up time after HPCT was 36.6 months. At 3 years, the estimated OS and PFS rates were 52% and 43%, respectively, for patients with indolent disease, and 18% and 21%, respectively, for patients with transformed disease. Patients with indolent disease and related donors (n = 26) had 3-year estimated OS and PFS rates of 67% and 54%, respectively. The incidences of grade 2 to 4 acute GVHD, grade 3 and 4 acute GVHD, and extensive chronic GVHD were 63%, 18%, and 47%, respectively. Intriguingly while the risk of relapse was increased in patients with transformed (HR = 4.85; 95% CI, 1.5 to 15; $P = .001$) or chemotherapy-refractory disease (HR = 5.37; 95% CI, 1.7 to 17; $P = .005$); however, chemotherapy sensitivity did not have a significant impact on OS or PFS. These data argue that allogeneic HPCT can produce durable disease-free survival in patients with chemotherapy refractory lymphomas.

1.4. Busulfan:

Busulfan, a potent, cytotoxic, bifunctional alkylating agent that causes myeloablation, has been used clinically since the 1950s to treat hematological malignancies and myeloproliferative syndromes. Busulfan produces deoxyribonucleic acid (DNA) cross-linking and chromosomal

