Fludarabine has a long plasma half-life, allowing once-daily administration. Fludarabine and once daily busulfan have demonstrated synergistic cytotoxicity [24]. Russell et al [25], have reported safety and efficacy data with a once-daily intravenous busulfan and fludarabine conditioning regimen for allogeneic HPCT in patients with hematologic malignancies. Their conditioning regimen comprised fludarabine 50 mg/m² on days -6 to -2 plus i.v. busulfan 3.2 mg/kg daily in a 3-hour infusion on days -5 to -2. The regimen was given to 70 patients aged 15 to 64 years (median, 41 years) with hematologic malignancy. Acute GVHD prevention comprised antithymocyte globulin 4.5 mg/kg over 3 days pretransplantation, cyclosporin A, and short-course methotrexate with folinic acid. Hepatic toxicity was transient and there was no clinically diagnosed veno-occlusive disease. Incidence of acute GVHD grades II to IV was 8% and chronic GVHD at 2 years is 38%. With a median follow-up of 16 months (range, 6-27 months), transplantation-related mortality at 100 days and 2 years was 2% and 5% for matched

related donor HPCT and 8% and 19% for alternate donors HSCT, respectively (P = not significant). Projected disease-free and OS rates at 2 years were 74% and 88% for low-risk disease, 26% and 37% for advanced AML, and 65% and 71% for other high-risk disease, respectively. Pharmacokinetic studies were done using 11 samples with the first and fourth doses of busulfan. Kinetics were linear, and for the first and fourth doses, the half-lives were 2.60 +/- 0.44 and 2.57 +/- 0.36 hours, respectively. Clearances were 106.77 +/- 16.68 and 106.86 +/- 21.57 mL/min per m², peak concentrations (Cmax) were 3.92 +/- 0.31 and 3.96 +/- 0.28 mcg/mL, and busulfan areas under the plasma concentration versus time curve (AUC) were 4866.51 +/- 771.42 and 4980 +/- 882.80 μ mol.min, respectively. Day 4 pharmacokinetic values were very similar to those on day 1 for every patient. That report demonstrated the combination to be efficacious, with impressively low treatment-related mortality.

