OS and progression free survival PFS will be estimated using the Kaplan-Meier method. OS is defined as the time from transplant to death, and surviving patients will be censored at last follow-up. PFS is defined as the time from transplantation to disease progression/relapse and/or death. OS and PFS data between subgroups will be analyzed by the log-rank test. NRM is defined as death from any cause other than disease progression or relapse. Cumulative incidences of NRM and relapse will be calculated with relapse or death as a competing event, respectively [37]. Comparisons between estimates of cumulative incidence will be made by using the Gray's test. The cumulative incidence of acute or chronic GVHD will be calculated with relapse or death without GVHD as competing events [37,38]. We anticipate that a maximum of 32 patients will be accrued to the study. Descriptive statistics (i.e. means, standard deviations, 95% confidence intervals for continuous variables, and frequencies for discrete data) will be computed for all correlative laboratory parameters. Given the small sample size in this phase II trial, a total of 32 patients limits our ability to perform inferential tests.

Accrual Estimate: 32 patients.

Accrual Period: Until 12/31/2013.

Safety/Stopping Rules:

Rates of non-relapse mortality and grade III-IV acute GVHD will be monitored on 6 monthly basis. The study will be halted for review by the data safety and toxicity committee (DSTC) if any of the following criteria are met.

1. Non-relapse mortality of >40% at day 100 after transplantation.
2. Cumulative incidence of grade III-IV acute GVHD is >40% at day 100 after transplantation.

Follow-Up Period : One year to evaluate progression free survival.

10. Records to be Kept:

Particular attention should be given to the specification of which data elements should be included in the Mary Babb Randolph Cancer Center Clinical Trials Research Unit OnCore database. The investigator will maintain adequate records in the Investigator Site File to enable the conduct of the study to be fully documented. All documents related to the conduct of the study will be kept on file in a readily accessible order. This file must be safely archived after the termination of the study.

Patient data collected on Case Report Forms (CRFs) should be sent to the Network Coordinator at the CTRU by fax at [contact] according to CRF submission guidelines provided by WVU. Data will be entered into the OnCore database.

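### The day-100 non-relapse mortality halt limit of 40% lies above every mortality figure the protocol cites, so it gives little protection against excess early mortality

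*Combined protocol and SAP*

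**What the plan says.** Section 9, under Safety/Stopping Rules, sets two criteria, either of which halts the study for review by the data safety and toxicity committee (DSTC):

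- "Non-relapse mortality of >40% at day 100 after transplantation"
- "Cumulative incidence of grade III-IV acute GVHD is >40% at day 100 after transplantation"

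On timing it says only: "Rates of non-relapse mortality and grade III-IV acute GVHD will be monitored on 6 monthly basis". It gives no minimum number of evaluable patients, no number of patients per look, no expected or accepted rate, and no probability that either rule will trigger. On size it says: "We anticipate that a maximum of 32 patients will be accrued to the study". NRM is defined in the same section as any death not due to progression or relapse.

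The background supplies these figures:

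- Section 1.5, once-daily IV busulfan-fludarabine in 70 patients with mixed hematologic malignancies: "transplantation-related mortality at 100 days and 2 years was 2% and 5% for matched" related donors, and 8% and 19% for alternate donors.
- Section 1.5, the AML/MDS series: 3% treatment-related mortality at 1 year.
- Section 1.3, the chemorefractory NHL series: overall NRM 34%, with 5-year median follow-up.
- Section 1.3, the relapsed/refractory DLBCL series: NRM 32% at 4 years.
- Section 1.3, the nonmyeloablative series: "The incidences of grade 2 to 4 acute GVHD, grade 3 and 4 acute GVHD, and extensive chronic GVHD were 63%, 18%, and 47%, respectively". No time point is given for the 18%.

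**The concern.** A halt limit on early mortality should lie somewhere above the rate that is expected and accepted, and close enough to it that a real excess is noticed within the planned sample. The NRM limit is not tied to any rate in the protocol. The quoted day-100 figures are 2% and 8%, and even the figures accumulated over 4 to 5 years in lymphoma stay below 40%. A rule that allows 40% by day 100 therefore tolerates more early death than any cited series reported over its whole follow-up.

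These two limits are the only numerical safety stops in a single-arm trial of a regimen described as reduced-toxicity. If the NRM rule rarely triggers when early mortality is two or three times the cited rate, completing accrual without a halt says little about whether early mortality was acceptable.

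**Working it through.** **Plan's own figure.** None exists for these rules. The only computed design figure in Section 9 concerns 1-year PFS and does not bear on this point.

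**Inputs.** From Section 9: limit 40%, N = 32, six-monthly review. From Sections 1.3 and 1.5: 2%, 8%, 34% and 18%. Assumed: every patient is evaluable at day 100, so the cumulative incidence equals the simple proportion, and the look sizes are as listed below. Seven looks is about the most that six-monthly review allows between protocol review approval (6/15/2010, Section 11.2) and the end of accrual (12/31/2013), roughly 3.5 years.

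**Step 1: ratio of limit to cited rates.** NRM: 40/8 = 5 and 40/2 = 20. Grade III-IV GVHD: 40/18 = 2.2.

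**Step 2: events needed to exceed 40%.** The smallest count c with c/n > 0.40 is:

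- one look, n = 32: 13
- four looks, n = 8, 16, 24, 32: 4, 7, 10, 13
- seven looks, n = 5, 9, 14, 18, 23, 27, 32: 3, 4, 6, 8, 10, 11, 13

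**Step 3: chance of ever halting.** For one look this is P(X ≥ 13) with X ~ Binomial(32, p). For several looks, let f_j(x) be the probability of x events at look j with no halt so far. Then f_j(x) = Σ_y f_(j−1)(y) · b(x − y; n_j − n_(j−1), p) for x < c_j, and the chance of halting is 1 − Σ_x f_J(x) at the last look J.

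| Endpoint and true rate | One look | Four looks | Seven looks |
|---|---|---|---|
| NRM 16% (2 × 8%) | 0.1% | 3.1% | 6.2% |
| NRM 24% (3 × 8%) | 2.8% | 14.4% | 21.3% |
| NRM 34% (all of the long-term NRM by day 100) | 27% | 47% | 55% |
| GVHD 18% | 0.2% | 4.9% | 8.9% |
| GVHD 36% (2 × 18%) | 35% | 55% | 62% |
| GVHD 54% (3 × 18%) | 95.5% | 97.6% | 98.1% |

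An 80% chance of halting needs a true rate of 46.5%, 43.1% and 41.6% respectively. Against 8% that is a 5.8-, 5.4- and 5.2-fold excess.

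**Step 4: sensitivity to very early looks.** One event in 1 or 2 patients already exceeds 40%. Adding a look at 1 patient, or starting at 2, raises halting at a true 24% to about 36-48%, but also raises it at a true 8% to about 8-16%. The gain comes largely from halts on a single early event.

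**Step 5: a boundary tied to an accepted rate p0.** Halt at the smallest k whose exact (Clopper-Pearson) one-sided 90% lower bound exceeds p0. The bound is the 0.10 quantile of Beta(k, n − k + 1). For example, 5/32 gives 0.078 and 6/32 gives 0.102, so p0 = 8% requires 6/32. Similarly 9/32 gives 0.177 and 10/32 gives 0.204, so p0 of 18% or 20% requires 10/32. With looks at 8, 16, 24 and 32:

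| Accepted rate | Halt at | Chance of halting by true rate |
|---|---|---|
| 8% | 3/8, 4/16, 5/24, 6/32 | 7% at 8%; 48% at 16%; 70% at 20%; 85% at 24%; 99% at 34% |
| 18-20% | 4/8, 6/16, 8/24, 10/32 | 11% at 18%; 17% at 20%; 76% at 34%; 82% at 36% |

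**The case against.** Five objections have force.

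- **Comparability.** The 2% and 8% are transplantation-related mortality in mixed malignancies, patients aged 15-64, with a fixed GVHD prophylaxis. This trial counts any death without relapse, in relapsed/refractory lymphoma up to age 70, with one HLA mismatch allowed and prophylaxis left to each center. No day-100 NRM for refractory lymphoma is quoted. These are therefore the closest available figures, not rates with the same definition. This stands, and it is why the accepted rate should come from the sponsor. It does not rescue 40%: if the chemorefractory series' entire 34% fell within 100 days, the rule would still halt only 27-55% of the time.
- **Other safeguards.** A reader might infer that excess deaths would pass without review. Section 10.1 sends every fatal expected event, and every unexpected grade 3-5 event, to the DSTC within 24 hours, and Section 5.8 has the committee review all serious adverse events. Deaths are seen one by one. What is missing is any other numerical threshold that turns them into a halt.
- **GVHD.** A reader might infer that both rules usually miss a two- to three-fold excess. For GVHD that is not so: three times 18% is 54%, above the limit and caught in 95-98% of trials, and a doubling is caught in 35-62%. The 18% itself comes from one nonmyeloablative series without a time point.
- **Origin of the 40%.** One might suspect it was borrowed from grade II-IV GVHD. The grade II-IV rates quoted are 8%, 17%, 43% and 63%, so only one of four is close. The documents do not say where 40% came from.
- **Look schedule.** The percentages depend on looks that the plan does not specify. This stands, and the range is shown above.

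**Conclusion.** The concern holds for the NRM limit. At 40% by day 100 it is 5 to 20 times the closest cited day-100 figures and above every NRM or treatment-related mortality figure in the protocol. At a true 24%, three times the higher cited figure, it halts about 3% of the time with one look, 14% with four and 21% with seven. At 16% the corresponding figures are 0.1%, 3% and 6%. The exact percentages assume those looks and full day-100 evaluability; only looks at one or two patients change them much, and those also add false halts.

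The GVHD limit is a secondary point: its protection against a doubling is uncertain, but it is adequate against a tripling. The documents support neither the claim that both rules fail alike nor the claim that early deaths would go unreviewed. The NRM rule should be corrected, but the trial is not without safety oversight in the meantime.

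**What to change.** In Section 9, Safety/Stopping Rules, have the sponsor state the day-100 NRM it accepts for this population. Replace the flat 40% with a halt for DSTC review when the exact one-sided 90% lower confidence bound exceeds that rate. State the look sizes and report the chance of halting over a range of true rates. The 8% and 18-20% boundaries worked out above are illustrations, not recommended rates. Even the 18-20% boundary needs 10/32 at full accrual instead of 13/32, although at 8 patients it equals the present rule (4/8) and at 16 it differs by one event (6 against 7). The same form can be used for grade III-IV GVHD.

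The change is a rewording, with no extra patients or procedures. Its price is unnecessary pauses. When toxicity is at the accepted rate, the chance is roughly 7-17% per rule. With the two rules set at 8% and 18%, the chance of at least one pause is about 1 − (1 − 0.074)(1 − 0.108) = 17%, assuming independence. If the accepted NRM is set too low for refractory lymphoma the cost rises: an 8% reference would pause 48-70% of trials at a true 16-20%.

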10.1. ADVERSE EVENTS: LIST AND REPORTING REQUIREMENTS

Definitions

The following are definitions of adverse events as defined by 21CFR312.32.

Types of Adverse Events

Adverse Event means any untoward medical occurrence associated with the use of a drug in humans, whether or not consider drug related.

Life-threatening adverse event or life-threatening suspected adverse reaction: An adverse event or suspected adverse reaction is considered “life-threatening” if, in the view of either the investigator or sponsor, its occurrence places the patient or subject at immediate risk of death. It does not include an adverse event or suspected adverse reaction that, had it occurred in a more severe form, might have caused death.

Serious adverse event or serious suspected adverse reaction: An adverse event or suspected adverse reaction is considered “serious” if, in the view of the investigator or sponsor, it results in any of the following outcomes:

- Death,
- A life-threatening prolongation of existing hospitalization,
- A persistent or significant incapacity or substantial disruption of the ability to conduct normal life functions, or
- A congenital anomaly/birth defect.

- Important medical events that may not result in death, be life-threatening, or require hospitalization may be considered serious when, based upon appropriate medical judgment, they may jeopardize the patient or subject and may require medical or surgical intervention to prevent of the outcomes listed above.

Suspected adverse reaction means any adverse event for which there is a reasonable possibility that the drug caused the adverse event. “Reasonable possibility” means there is evidence to suggest a causal relationship between the drug and the adverse event. Suspected adverse reaction implies a lesser degree of certainty about causality than adverse reaction, which means any adverse event caused by a drug.

Unexpected adverse event or unexpected suspected adverse reaction: An adverse event or suspected adverse reaction is considered “unexpected” if it is not listed in the investigator brochure or is not listed at the specificity or severity that has been observed; or, if an investigator brochure is not required or available, it is not consistent with the risk information currently described.

Unexpected also refers to adverse events or suspected adverse reactions that are mentioned in the investigator brochure as occurring with a class of drugs or as anticipated from the pharmacological properties of the drug, but are not specifically mentioned as occurring with the particular drug under investigation.

Adverse Event Grading

Grade	Description
0	No AE (or within normal limits).
1	Mild ; asymptomatic or mild symptoms; clinical or diagnostic observations only; intervention not indicated.
2	Moderate ; minimal, local or noninvasive intervention (e.g., packing cauter) indicated; limiting age-appropriate instrumental activities of daily living (ADL).
3	Severe or medically significant but not immediately life-threatening; hospitalization or prolongation of hospitalization indicated; disabling;

limiting self-care ADL.

4 **Life-threatening** consequences; urgent intervention indicated.

5 **Death** related to AE

Adverse Event Attribution

Relationship	Attribution	Description
Unrelated to investigational agent/intervention	Unrelated	The AE is clearly NOT related to the intervention
	Unlikely	The AE is doubtfully related to the intervention
Related to investigationl agent/intervention	Possible	The AE may be related to the intervention
	Probable	The AE is likely related to the intervention
	Definite	The AE is clearly related to the intervention

Reporting of Adverse Events

Because all of the study transplant recipients will be receiving potentially toxic preparative therapy, significant regimen related toxicity is expected. These risks are listed in the consent form. A study specific toxicity CRF will be designed to capture information regarding these expected events. Transplant is also related to a degree of mortality and this will also be captured by a study designed CRF. Unexpected adverse events will be reported throughout the study.

Unexpected Adverse Events

Grades 3-5 (severe, life threatening, disabling, or fatal) require expedited reporting and will be submitted to the DSTC within 24 hours of discovery for review. If the Grade 3-5 event is determined to be an unanticipated problem, the event will be forwarded to the WVU IRB for review as required by their policy. Unexpected adverse events, regardless of severity, will be reported to the DSTC and reviewed on a quarterly basis.

Expected Adverse Events

All fatal (grade 5) expected adverse events require expedited reporting and will be reported to the DSTC within 24 hours for review. Expected adverse events that are being captured on the study toxicity form will be reported at the time of the form's scheduled due date.

All DSTC reports and recommendations will be submitted to the IRB for their review.

Adverse Events Occurring after the End of the Study

Follow-up of AEs

Any unexpected AEs ongoing at the time of study discontinuation will be followed until resolution or stable for at least 2 months.

FDA Reporting Procedures

Commercial Agents: Commercial agents are those agents not provided under an IND but obtained instead from a commercial source. In some cases an agent obtained commercially may be used for indications not included in the package label. The following procedures should be followed to determine if an adverse is reportable to the FDA:

Refer to the pharmaceutical section of the protocol to determine if an agent is investigational or commercial.

- **WHAT TO REPORT:** An unexpected, life-threatening (Grade 4) or unexpected, fatal (Grade 5) adverse event with an attribution of possible, probable or definite.
- **WHEN TO REPORT:** These events should be reported within (7) working days.
- **WHERE TO REPORT:** These adverse events with commercial agents must be reported to the FDA using the MedWatch form. A copy of the MedWatch form can be obtained from the FDA's MedWatch web site at www.fda.gov/medwatch. You can mail the reports to the address below or fax it [name].

MedWatch
[name]
[name]

11. Patient Consent and Peer Review Statement

11.1. Subject Information and Informed Consent

Written informed consent must be obtained from the subject prior to study participation.

The informed consent document must be signed and dated by the subject and properly witnessed (if applicable) before initiation of any study procedures including any change in medication or initiation of study drug dosing.

Subjects must be consented in accordance with all local regulatory and legal requirements. This process must include a verbal explanation of the nature, scope, and possible consequences of the study provided in plain language. The information should be presented by the investigator unless a designee is permitted by local regulations. The potential study subject should be encouraged to ask questions about the study.

The informed consent document must be prepared in accordance with GCP guidelines and with local regulatory and legal requirements. A copy of the signed consent form will be given to the subject and the original document must be safely archived by the investigator so that the forms can be retrieved at any time for monitoring, auditing, and inspection purposes.

The informed consent will be updated as appropriate (e.g., due to protocol amendment or if significant new safety information that may be relevant to consent of the subjects becomes available). If the informed consent is revised, it is the investigator's responsibility to ensure that an amended consent form is reviewed and signed by all subjects subsequently entered into the study and those currently in the study, if applicable per local IRB and/or federal requirements.

